6.4. Covariates and Subgroups

As a protocol defined exploratory analysis, HAI antibody response following the second vaccination will be summarized stratified by the following covariates: age (categorical: 19-34, 35-49, 50-64), sex (male, female), body mass index (<30 , ≥ 30), and prior receipt of seasonal influenza vaccine(s) (received 2016-2017, did not receive 2016-2017, unknown), and these covariates will be considered in statistical modeling as described in Section 8.3. As these analyses are exploratory the study was not powered for any subgroup analyses.

6.5. Missing Data

All attempts will be made to collect all data per protocol. As missing data are expected to be minimal, no imputation will be performed for missing values. Any data point that appears to be erroneous or inexplicable based on clinical judgment will be investigated as a possible outlier. If data points are identified as outliers, sensitivity analyses will be performed to examine the impact of including or excluding the outliers. Any substantive differences in these analyses will be reported.

6.6. Interim Analyses and Data Monitoring

Interim analyses will only be used to terminate this trial in the event that unanticipated safety events deemed to be of sufficient concern require such action by the sponsor. These assessments will not be made on the basis of testing a formal statistical hypothesis; therefore, p-value adjustment will not be made to any analyses. A DSMB will be convened by DMID to review study progress and participant, clinical, safety, and reactogenicity and immunogenicity data.

A preliminary report of safety and immunogenicity data through Day 64 will be prepared as described in section protocol section 11.6; though this report will be released while subjects remain in the trial for long-term safety and immunogenicity follow-up, it will be considered the final analysis of these data.

Emergent public health needs may dictate additional interim safety, reactogenicity, and/or immunogenicity analyses be performed on available information at any time during the trial. If this occurs, immunogenicity data will be analyzed as results are available from the central immunogenicity laboratory.

6.6.1. Interim Safety Review

An interim safety review may include enrollment and demographic information, medical history, concomitant medications, physical assessments, clinical laboratory values, dosing compliance, and solicited and unsolicited AE/SAEs. Additional data may be requested by the DSMB, and interim statistical reports may be generated as deemed necessary and appropriate by DMID. The DSMB may receive data in aggregate and presented by treatment group. The DSMB may also be provided with expected and observed rates of the expected AEs by

treatment group, and may request the treatment assignment for an individual subject if required for safety assessment. The DSMB will review data grouped by treatment group in the closed session only. The DSMB will meet and review this data at scheduled time points or ad hoc as needed during this trial as defined in the DSMB charter. As an outcome of each review/meeting, the DSMB will make a recommendation as to the advisability of proceeding with study vaccinations (as applicable), and to continue, modify, or terminate this trial. Summaries prepared for the DSMB are defined separately in a report shell reviewed and approved by the DSMB.

Additionally, this trial will be monitored to determine if any of the halting rules described in Protocol Section 9.5 are met.

6.6.2. Interim Immunogenicity Review

No interim immunogenicity analysis is planned. Should emergent public health needs dictate immunogenicity review, immune responses will be summarized in terms of strain-specific 2017 A/H7N9 and IIV4 HAI and Neut antibody titers for subjects that receive sequential or simultaneous administration of AS03-adjuvanted 2017 H7N9 IIV and seasonal IIV4. It is anticipated that all analyses will be carried out in parallel for both assays, but reports may be prepared separately for HAI and Neuts if results are available on different timelines. Interim analyses will focus on rates of titers $\geq 1:40$, seroconversion (see definition in Section 3.3) and GMTs, along with corresponding 95% CIs. No formal hypothesis testing will be included in the interim analysis, and interim results will not have impact on conduct of this trial.

Any immunogenicity reports would be provided by the SDCC to the DMID Scientific Lead and Clinical Project manager, and the DSMB. Reports will include data summarized by treatment group.

6.7. Multicenter Studies

Randomization was stratified by site, but data will be pooled across all clinical sites for all analyses. Center effects are not anticipated because the sites use standardized procedures for vaccination and assessment of solicited and unsolicited AEs, and the study relies on a central laboratory for immunogenicity assessments.

6.8. Multiple Comparisons/Multiplicity

This study was designed to obtain preliminary estimates of safety and immune response to A/H7N9 and IIV4 vaccination in healthy adults. The study was not designed to test any specific null hypothesis, and as such no adjustment for multiple comparisons will be performed.

7. STUDY SUBJECTS

7.1. Subject Disposition

[Table 17](#) will present a summary of the reasons that subjects were screened but not enrolled.

The number and percentage of enrolled subjects excluded from each analysis population by treatment group are presented in [Table 18](#). A listing of subjects excluded from each analysis population will be presented in [Listing 5](#).

The disposition of subjects in the study will be tabulated by treatment group ([Table 19](#)). The table will show the total number of subjects screened, randomized, receiving the first dose, receiving the second dose, receiving the third dose, completing the blood draw for the primary immunogenicity endpoints, and completing the last visit.

A flowchart showing the disposition of study subjects, adapted from the CONSORT Statement [4] will be included and will present the number of subjects screened, randomized, lost to follow up, and analyzed, by treatment group ([Figure 1](#)).

A listing of subjects who were discontinued from treatment or terminated from study follow-up and the reason will be included in [Listing 2](#).

7.2. Protocol Deviations

A summary of subject-specific protocol deviations will be presented by the deviation category and deviation type, and treatment group for all enrolled subjects ([Table 12](#)). Major deviations that will be reviewed for possible exclusion of immunogenicity results from the PP population include deviations related to eligibility/enrollment, treatment administration schedule, follow-up visit schedule, and receipt of exclusionary vaccines or medications. All subject-specific protocol deviations and non subject-specific protocol deviations will be included in [Listing 3](#) and [Listing 4](#).

8. IMMUNOGENICITY EVALUATION

Immunogenicity data summaries and analysis for primary and secondary endpoints will be presented for the mITT and PP populations. Immune responses in terms of strain-specific A/H7N9 HAI and Neut antibody titers will be summarized by treatment group at each time point. Descriptive summary statistics will be provided for all assays and time points including number of subjects with non-missing results, percentage of subjects with titers $\geq 1:40$, percentage of subjects achieving seroconversion, and GMTs along with corresponding 95% CI. Exact confidence intervals will be presented for proportional endpoints. Summaries of primary and secondary immunogenicity endpoints are presented for the 2017 H7N9 strain in [Table 28](#), [Table 29](#), [Table 30](#), and [Table 31](#) and for the seasonal IIV4 strain in [Table 32](#), [Table 33](#), [Table 34](#), and [Table 35](#).

Reverse cumulative distribution (RCD) curves will be presented for post-vaccination HAI and Neut antibody titers. Plots for each assay will be generated with 5 panels (21 days post dose 1, 21 days post dose 2, 21 days post dose 3, 180 days post dose 1, and 180 days post final dose), and separate curves within each panel for each treatment group, as shown in [Figure 2](#), [Figure 3](#), [Figure 4](#), and [Figure 5](#) for the 2017 A/H7N9 strain. RCD curves for the IIV4 strains will be presented as in [Figure 6](#), [Figure 7](#), [Figure 8](#), [Figure 9](#), [Figure 10](#), [Figure 11](#), [Figure 12](#), [Figure 13](#), [Figure 14](#), [Figure 15](#), [Figure 16](#), [Figure 17](#), [Figure 18](#), [Figure 19](#), [Figure 20](#), and [Figure 21](#).

Figures depicting the HAI and Neut GMT over time will also be presented as shown in [Figure 22](#), [Figure 23](#), [Figure 24](#), and [Figure 25](#) for the 2017 A/H7N9 strain, and for the IIV4 strains in [Figure 26](#), [Figure 27](#), [Figure 28](#), [Figure 29](#), [Figure 30](#), [Figure 31](#), [Figure 32](#), [Figure 33](#), [Figure 34](#), [Figure 35](#), [Figure 36](#), [Figure 37](#), [Figure 38](#), [Figure 39](#), [Figure 40](#), and [Figure 41](#).

The spearman correlation between HAI and Neut antibody titers will be calculated at each time point over all groups. The correlation will be depicted in scatter plots as [Figure 42](#) and [Figure 43](#) for the 2017 A/H7N9 strain. Scatterplots depicting correlation for the IIV4 strains will be created as [Figure 44](#), [Figure 45](#), [Figure 46](#), [Figure 47](#), [Figure 48](#), [Figure 49](#), [Figure 50](#), and [Figure 51](#).

Individual HAI and Neut assay results will be provided in [Listing 8](#).

8.1. Primary Immunogenicity Analysis

The primary immunogenicity endpoints HAI and Neut seroconversion, percentage of subjects with titer $\geq 1:40$, and GMTs against the seasonal IIV4 strains 21 days after the IIV4 vaccination for all groups and against the homologous A/H7N9 vaccine strain 21 days after the second dose of AS03 adjuvanted 2017 H7N9 IIV will be summarized as described above. The primary analysis population will be mITT, with results from the PP population providing a comparison of the sensitivity of immunogenicity results to subject adherence to protocol-

defined conditions. Regression modelling of seroconversion and log titers is planned as described in Section 8.3.2.

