11 STATISTICAL CONSIDERATIONS

11.1 Introduction

The goal of this clinical trial is to assess, in healthy adults ages 19 – 64, the safety, reactogenicity, and immunogenicity of a pre-pandemic AS03-adjuvanted 2017 H7N9 IIV when two doses are administered 21 days apart either sequentially or simultaneously (within 15 minutes) with licensed seasonal influenza vaccine. Primary immunogenicity objectives include evaluating interference with response to 2017 H7N9 IIV vaccine virus strain 21 days post dose 2, and evaluating interference with response to seasonal influenza virus strains 21 days post receipt of IIV4.

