11.4.3 Sample Size

This study is planned to enroll a minimum of 60 subjects in Groups 1-2, and 30 subjects in Group 3. This study is not designed to test a formal null hypothesis. Rather, it is intended to obtain sufficient data to obtain meaningful estimates of the immune response and to uncover any safety issues that occur at a sufficiently high rate that they might be observed in a study of this size. As such, the type one error rate, alpha = 0.05, is not adjusted for multiple comparisons.

While this study is not designed to test any specific null hypothesis, the following tables illustrate the precision and power for select estimates and comparisons of interest.

[Table 3](#) indicates the probability of observing one or more safety events, such as solicited injection site or systemic reactogenicity events or an unsolicited non-serious AE of a particular type for a single treatment arm (N = 30 or 60), and for all subjects receiving AS03-adjuvanted 2017 H7N9 IIV (N = 120).

Table 3: Power (%) to Detect Safety Events:

Event Frequency	N = 30	N = 60	N = 120
≥10% Very Common	96	>99	>99
≥1%	26	45	70

Common			
$\geq 0.1\%$ Uncommon	3	6	11
$\geq 0.01\%$ Rare	<1	<1	1

Binomial confidence intervals (CI) are widest (have the least precision) when the response rate is 50%. [Table 4](#) is presented to indicate the worst-case scenario for precision of observed exact (Clopper-Pearson) binomial confidence intervals.

Table 4: Precision of Binomial Confidence Intervals:

N	95% CI
30	31-69
60	37-63
120	40-60

For each of the primary immunogenicity objective, a power analysis is provided below for testing the following hypotheses with the planned sample size, where p_c = proportion responders in comparator arm; p_e = proportion responders in experimental arm.

Test for difference in proportion responders:

$H_0: p_c - p_e = 0$ – No difference in proportion responders

$H_1: p_c - p_e \neq 0$ – difference in response rates

[Table 5](#) and [Table 6](#) present the minimum detectable differences in the proportion of subjects responding (e.g., attaining seroconversion or a titer $\geq 1:40$) between two treatment arms using a two-sided Likelihood Ratio Test and alpha = 0.05.

Primary Immunogenicity Objective 1: Evaluate antibody responses against A/H7N9 at approximately 21 days following receipt of two doses of AS03-adjuvanted 2017 H7N9 IIV. Comparison between simultaneous and sequential receipt to IIV4, i.e., Group 1 at Day 43 vs. Group 2 at Day 64.

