11.6.3 Immunogenicity Data

Summaries and analysis of immunogenicity data will be presented for the mITT and PP populations.

Immune responses in terms of 2017 H7N9 or IIV4 strain-specific HAI and Neut antibody titers will be summarized by treatment arm at each time point. Analyses will include number and percentage of subjects with a titer $\geq 1:40$, number and percentage of subjects achieving seroconversion (defined as either a pre-vaccination titer < 10 and a post-vaccination titer $\geq 1:40$ or a pre-vaccination titer $\geq 1:10$ and a minimum four-fold rise in post-vaccination antibody titer), and GMTs along with corresponding 95% CIs. Descriptive summary statistics will be provided for all assays and time points. The correlation between HAI and Neut antibody titers will be evaluated. Plots such as reverse cumulative distributions or longitudinal presentations of GMTs will be presented.

Additionally, the immune response, as described above, will be summarized by available covariates, such as age, sex, BMI, and prior receipt of seasonal influenza vaccine(s), and these covariates may be considered statistical modeling. As an exploratory analysis, models may be developed to evaluate the relationship between study vaccination schedule and immune response.

Additionally, N1, N2 and N9 NA-specific antibody assays are in development. If successful, N1, N2 and N9 NA-specific responses may be assessed at baseline, 21, 42, 63, and 180 days after receipt of the first study vaccination. For each time point, summaries may include number

and percentage of subjects with detectable N1, N2 and N9 NA response (to be defined in SAP based following assay development and selection) and GMTs along with corresponding 95% CIs. Descriptive summary statistics will be provided for all assays and time points. The correlation of N1, N2 and N9 NA response with HAI and Neut antibody titers will be evaluated, and plots such as reverse cumulative distributions or longitudinal presentations of GMTs will be presented.

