8.3.2. Regression Modeling

Logistic and multivariate linear regression will be utilized to test for the effects of the treatment schedule on seroconversion and GMT against the homologous 2017 A/H7N9 strain and against each of the seasonal IIV4 strains for the PP population. Similar models will be fit for HAI and Neut Antibodies for each strain and time point. Separate models will be fit for data from Day 21 post dose and Day 180 post dose.

Logistic regression will be fit to examine the relationship of HAI or Neut seroconversion at 21 or 180 days after the dose of interest (second dose of AS03 adjuvanted A/H7N9 IIV for the 2017 A/H7N9 strain; IIV4 vaccination for the seasonal IIV4 strains) with treatment schedule. If the available titer data meets the required assumptions of normality after log

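### The SAP names mITT as the primary immunogenicity population, but every planned between-group estimate at 21 days (16 tables, 40 models) is fitted on the per-protocol population

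*SAP*

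**What the plan says.** SAP 8.1 (Primary Immunogenicity Analysis) says: "The primary analysis population will be mITT, with results from the PP population" used to see how far the results depend on adherence. The paragraph ends: "Regression modelling of seroconversion and log titers is planned as described in Section 8.3.2".

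SAP 8.3.2 fits logistic models for seroconversion and linear models for log titre, against the H7N9 strain and "against each of the seasonal IIV4 strains for the PP population". It sits under SAP 8.3, which places exploratory endpoints on PP. The titles of Tables 68-99 all name the Per Protocol population.

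Two general statements cover both populations. SAP 8 says: "Immunogenicity data summaries and analysis for primary and secondary endpoints will be presented for the mITT and PP populations". Protocol 11.6.3 says: "Summaries and analysis of immunogenicity data will be presented for the mITT and PP populations". On the models themselves, Protocol 11.6.3 says: "As an exploratory analysis, models may be developed to evaluate the relationship between study vaccination schedule and immune response".

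The objective is comparative. Protocol 11.1 says: "Primary immunogenicity objectives include evaluating interference with response to 2017 H7N9 IIV vaccine virus strain 21 days post dose 2", and adds the same aim for the seasonal strains after IIV4. Protocol 11.4.3 names the H7N9 contrast: "Comparison between simultaneous and sequential receipt to IIV4, i.e., Group 1 at Day 43 vs. Group 2 at Day 64".

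**The concern.** Interference can be judged only by comparing groups. The plan names one population as primary and then takes all its between-group estimates from the other, which it has called the sensitivity set. The stated reason for having two populations is to show whether results depend on adherence. With the models on PP alone, that check is not available for the comparative result.

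This matters for reporting. SAP 6.2.1 treats analyses in the Preliminary Report as final for those data and allows their release for publication. Most of the 21-day model tables are marked for that report, with no mITT counterpart.

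**Working it through.** **1. The plan's own comparative figures.** Protocol Table 5 gives detectable differences of 0.27, 0.27, 0.27, 0.26 and 0.22 for comparator rates 0.50 to 0.90, with 50 per group, 80% power and a two-sided likelihood ratio test at 0.05. The approximate noncentrality is 2 × Σ n[p ln(p/p̄) + (1−p) ln((1−p)/(1−p̄))], summed over the two groups. For 0.50 against 0.23, p̄ = 0.365, the noncentrality is 8.01 and power is 0.808. By exact binomial enumeration, power at the stated differences is 0.798-0.813 for Table 5 and 0.788-0.816 for Table 6 (75 against 50). The figures reproduce. They illustrate between-group comparisons for both primary immunogenicity objectives.

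**2. Models at 21 days** (SAP list of tables and shells).
- H7N9, one strain per table: Tables 68, 70, 76, 78, 84, 86, 92, 94. 8 × 1 = 8 models.
- IIV4, four strains per table: Tables 72, 74, 80, 82, 88, 90, 96, 98. 8 × 4 = 32 models.
- Total: 16 tables, 40 models.
- Cross-check: 2 assays × 5 strains × 2 endpoints × 2 (with and without covariates) = 40.
- Population: 40 of 40 on PP, 0 on mITT.
- 20 are logistic. The other 20 are linear and are fitted only if log titres pass a normality check (SAP 8.3.2).

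**3. What mITT receives.** Tables 28, 30, 32 and 34 give, by group, n, GMT, seroconversion and titre ≥1:40 with 95% CIs. The mITT figures show distributions, GMTs over time and HAI/Neut scatter plots. None contains a contrast between groups.

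**4. Preliminary Report.** In the list of tables, 14 of the 16 carry the mark (all but 70 and 98).

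**5. Does the PP restriction imply a bias for H7N9?** Before the primary sample, Group 1 has one later dosing visit and 43 − 1 = 42 days; Group 2 has two and 64 − 1 = 63 days. PP exclusion could therefore differ by arm. But SAP 6.3.2 and 6.3.3 both move Group 2 subjects who stop before H7N9 into Group 3, so they leave the H7N9 contrast in either population. As an illustration, assume that all exclusions are discontinuations, that the loss L is equal at each later dosing visit, and that Group 2 reaches the 15% ceiling in Protocol 11.4.2:
- (1 − L)² = 0.85, so L = 1 − √0.85 = 0.078.
- Group 1 loses 7.8% between mITT and PP.
- Group 2 has 92.2% left after reassignment and loses a further 15.0 − 7.8 = 7.2, and 7.2/92.2 = 7.8%.

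The fractions are equal, and would be for any L, because L(1 − L)/(1 − L) = L. If excluded and retained subjects also differ equally in both arms and all have samples, moving from PP to mITT changes the contrast by zero.

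**6. IIV4 at Day 22.** The sample is drawn before Dose 2, and SAP 6.3.3 removes only visits after a dosing deviation. A missed or late Dose 2 or 3 cannot affect it. For these 32 models the issue is a population mismatch only.

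**The case against.** The strongest reply is that nothing conflicts. SAP 8.1 promises summaries with mITT primary, and Tables 28, 30, 32 and 34 deliver them, with PP counterparts. The cross-reference leads to a section labelled exploratory and specified on PP. Protocol 11.6.3 makes the models optional, and Protocol 11.2 and SAP 6.8 say that no formal null hypothesis is tested. The 50 per group in Protocol Table 5 itself reflects PP losses (60 × 0.85 = 51). A reader could also derive a crude difference from the mITT tables.

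Much of this stands. The descriptive mITT analysis exists, and the exploratory label is in both documents. It does not explain why the models are cited under the primary analysis, or why analysis promised for both populations becomes PP only for every contrast. A difference worked out by hand from two displayed intervals is not a planned estimate with its own CI, and it cannot give the covariate-adjusted result. Calling the models exploratory and PP-based in 8.1 would end the ambiguity but leave mITT without a comparison.

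A reader might infer that the PP restriction distorts the interference result, since Group 2 has more doses and more time in which to be excluded. The documents do not support that. Step 5 shows that the change can be zero. They give neither the share of excluded subjects with a sample at the primary timepoint nor any response difference between excluded and retained subjects. Protocol 5.2.4 asks those who miss a dose for blood about 21 days after their last vaccination, which can fall before the primary sample.

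**Conclusion.** The inconsistency is real and should be corrected. Of 40 between-group models at 21 days, none uses the population named primary. This rests on the text of SAP 8.1 and 8.3.2 and on the table titles, not on assumptions.

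Its reach is limited. Only the 8 H7N9 models could be affected by dose-related exclusion that differs by arm. The size and direction of any effect are unknown, so no numerical shift should be quoted. Nor should this be read as a confirmatory test run on the wrong population, because the plan has no confirmatory test. The case rests on the missing mITT comparison for a primary objective.

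**What to change.** - Fit Models 1A-2B for the 21-day endpoints on mITT (SAP 6.3.2) as the main estimates with 95% CIs, not as confirmatory tests. Keep the existing PP fits as the sensitivity analysis.
- State the models' role and population in the same words in SAP 8.1 and 8.3.2.
- For the H7N9 contrast, add a check that keeps Group 2 subjects who stop before H7N9 in their randomised group where they have a sample.
- Leave the Day-180 models on PP; they are exploratory and agree with SAP 8.3.

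The cost is SAP wording, reruns of existing programs and up to 16 more tables. No new data are needed. Because PP is a subset of mITT, the models have no fewer subjects overall.

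A separate, minor display point: Tables 28-31 are laid out by study dose and Figures 2-5 by time from Dose 1. The row or panel 21 days after Dose 2 therefore sets Group 1 after two H7N9 doses beside Group 2 after one. Aligning by number of H7N9 doses would put Group 1 Day 43 and Group 2 Day 64 together.
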